COVID-19	Coronavirus Disease 2019
CRP	C-Reactive Protein
CSR	Clinical Study Report
CTL	Cytotoxic T Lymphocyte
DIBD	Development International Birth Date
DIC	Disseminated Intravascular Coagulation
DNA	Deoxyribonucleic Acid

Clinical Trial Protocol

Trial ID: CT-AMT-060-01

uniQure

Abbreviation	Definition
DSUR	Development Safety Update Report
eCRF	electronic Case Report Form
EMA	European Medicines Agency
EU	European Union
FDA	Food and Drug Administration
FIX	coagulation Factor IX
γ GT	gamma-Glutamyl Transpeptidase
gc	genome copies
GCP	Good Clinical Practice
GLP	Good Laboratory Practice
GMP	Good Manufacturing Practice
HBeAg	Hepatitis B extracellular Antigen
HBsAg	Hepatitis B surface Antigen
HBV DNA	Hepatitis B Virus Deoxyribonucleic Acid
HCV RNA	Hepatitis C Virus Ribonucleic Acid
HD-Ad	Helper Dependent Adenovirus
hFIX	human coagulation Factor IX
hFVIII	human coagulation Factor VIII
HIV	Human Immunodeficiency Virus
ICH	International Council for Harmonisation of Technical Requirements for Pharmaceuticals for Human Use
IEC	Independent Ethics Committee
IgG	Immunoglobulin G
IgM	Immunoglobulin M
IL-1 β	Interleukin-1beta

Clinical Trial Protocol

Trial ID: CT-AMT-060-01

Abbreviation	Definition
IL-2	Interleukin-2
IL-6	Interleukin-6
IMP	Investigational Medicinal Product
IND	Investigational New Drug
INF γ	Interferon gamma
INR	International Normalized Ratio
IRB	Institutional Review Board
IU	International Unit
MCP-1	Monocyte Chemotactic Protein-1
MedDRA	The Medical Dictionary for Regulatory Activities
mL	millilitre
mRNA	messenger Ribonucleic Acid
NCI	National Coordinating Investigator
nr LAM PCR	non-restrictive Linear Amplification Mediated Polymerase Chain Reaction
OTC	Over the Counter
PBGD	Porphobilinogen Deaminase
PCR	Polymerase Chain Reaction
PT	Prothrombin Time
CCI	CCI
Q-PCR	Quantitative Polymerase Chain Reaction
qs	sufficient quantity
rAAV	recombinant Adeno-Associated Virus
SAE	Serious Adverse Event
SAP	Statistical Analysis Plan

Clinical Trial Protocol

Trial ID: CT-AMT-060-01

Abbreviation	Definition
SARS-CoV-2	Severe acute respiratory syndrome coronavirus 2
SD	Standard Deviation
SDV	Source Data Verification
CCI	CCI
SPC	Summary of Product Characteristics
SUSAR	Suspected Unexpected Serious Adverse Reaction
US	United States of America
VG	Vector Genomes
WHO-DD	World Health Organisation Drug Dictionary
WNL	Within Normal Limits
w/w	weight per weight

Clinical Trial Protocol

Trial ID: CT-AMT-060-01

1. Sponsor's Approval of the Clinical Trial Protocol

4.1 Primary Objective

The primary objective of this trial is to investigate the safety of systemic administration of AAV5-hFIX, an adeno-associated viral (AAV) vector containing a codon-optimized human coagulation Factor IX (hFIX) gene, to adult patients with severe or moderately severe haemophilia B.

The primary objective will be assessed based on adverse events (AEs).

4.2 Secondary Objectives

Secondary objectives will be addressing efficacy and safety of systemic administration of AAV5-hFIX.

4.3 Trial Design

This trial has an open-label, uncontrolled, single-dose, dose-ascending design and consists of 2 cohorts. The trial will be conducted at multiple centres in multiple countries.

At study completion, subjects will be invited to participate in a separate long-term follow-up study that will collect efficacy and safety data up to 10 years from the IMP dosing date.

4.4 Trial Population

Male patients, aged ≥ 18 years, with severe or moderately severe haemophilia B with a severe bleeding phenotype defined as:

- Known coagulation Factor IX (FIX) deficiency with plasma FIX activity level $< 1\%$ (severe) or plasma FIX activity level $\geq 1\%$ and $\leq 2\%$ (moderately severe) and
- currently on prophylactic FIX replacement therapy for a history of bleeding, or
- currently on on-demand FIX replacement therapy with a current or past history of frequent bleeding (defined as 4 or more bleeding episodes in the last 12 months or chronic haemophilic arthropathy [pain, joint destruction, and loss of range of motion] in one or more joints).

Patients should have had more than 150 previous exposure days of FIX replacement therapy.

4.5 Intervention

The Investigational Medicinal Product (IMP) is a recombinant adeno-associated viral vector of serotype 5 (AAV5) containing the codon-optimized hFIX complementary deoxyribonucleic acid (cDNA) under the control of a liver-specific promoter. The IMP is identified as AAV5-hFIX. The pharmaceutical form of AAV5-hFIX is a solution for intravenous infusion.

Subjects will be allocated to one of 2 cohorts with the following planned dose levels:

- Cohort 1 (5 subjects): AAV5-hFIX 5×10^{12} gc/kg
- Cohort 2 (5 subjects): AAV5-hFIX 2×10^{13} gc/kg

Clinical Trial Protocol

Trial ID: CT-AMT-060-01

uniQure

The process for cohort allocation is described in [Section 11.2.1](#). Subjects will receive the IMP on only one occasion and will thereafter be followed for 5 years with respect to safety and with respect to efficacy measured as levels of FIX, bleeding patterns and consumption of FIX replacement therapy.

4.6 Interim Analyses

Interim analyses will be performed at the request of the data monitoring committee and at the request of the sponsor to enable reporting of adequate data at selected time points during the course of the trial. Descriptive statistics alone will be used for the interim analyses.

Clinical Trial Protocol

Trial ID: CT-AMT-060-01

uniQure

5. Schedule of Trial Procedures

Subjects will attend a screening visit (Visit 1) at a maximum of 6 weeks prior to the anticipated dosing visit (Visit 2). When the screening visit blood sample analysis results from the local and central laboratory are available, and it is confirmed that the subject is fulfilling the trial eligibility criteria, the dosing visit can occur provided that the intra- and inter-cohort staggering principles are adhered to (see [Section 10.1](#)). Sufficient time should be allowed for IMP shipment and preparation.

In case the subject no longer fulfils the eligibility criteria at the time of the dosing visit, re-screening is allowed as detailed in [Section 10.2.1](#).

After IMP administration, subjects will be monitored for tolerance to the IMP and detection of potential immediate AEs at the clinical trial site for 24 hours (overnight stay). Thereafter, subjects will be followed with respect to safety and efficacy parameters for 5 years (260 weeks) as follows:

- Twice weekly up to week 12
- Every 2nd week from week 12 to week 26
- Every 13th week from week 26 to week 156 (6 months to 3 years)
- Every 26th week from week 156 to week 260 (3 years to 5 years)

Clinical procedures to be performed in the period up to week 26 are listed in [Table 5-1](#).

Clinical procedures to be performed after week 26 and up to week 260 are listed in [Table 5-4](#).

Laboratory parameters to be measured in the period up to week 26 are listed in [Table 5-2](#).

Laboratory parameters to be measured after week 26 and up to week 260 are listed in [Table 5-5](#).

Clinical procedures to be performed in relation to IMP administration and the subsequent 24 hour observation period at the clinic (Visit 2) are listed in [Table 5-3](#).

Adjustments to the visit location or schedule may be made to accommodate safety concerns and restrictions due to the Coronavirus Disease 2019 (COVID-19) pandemic. In all cases, subjects will be kept informed as much as possible, of changes to the study and monitoring plans that could impact them.

Clinical Trial Protocol

Trial ID: CT-AMT-060-01

Table 5-1, Flow Chart for Safety and Efficacy Evaluation, Visits 1 - 21

Visit Number	1 Screening	2 ¹⁾ Day 1	2 ¹⁾ Day 2	3 to 14 (every week)	3 ^b to 14 ^b (every week)	15 to 20 (every 2 nd week)	21	Additional visits ²⁾
Weeks ⁴⁾	-6	0	0	1, 2, 3, 4, 5, 6, 7, 8, 9, 10, 11, 12	1, 2, 3, 4, 5, 6, 7, 8, 9, 10, 11, 12	14, 16, 18, 20, 22, 24	26	
Visit window ⁴⁾				±2 days	1-4 days after main weekly visit	±5 days	±5 days	
Informed consent	x							(x) ³⁾
Inclusion/exclusion criteria	x	x						(x) ³⁾
24 hour stay at clinic		x	x					
Administration of IMP		x						
Tapering prophylactic FIX replacement therapy (see Section 11.4) ⁵⁾				X (Visits 8-14 / weeks 6-12)				
Demographics and medical history ⁶⁾	x							
History and status of bleeding	x							
History of surgery	x							
Joint status	x							(x) ²⁾
Subject e-diary instruction	x	x						
Subject e-diary interview (including re-instruction, if needed)		x	x	x		x	x	(x) ²⁾
Review of e-diary data (bleeding episodes, FIX replacement therapy)		x	x	x		x	x	(x) ²⁾
Registration of severity of bleeding episode(s)		x	x	x		x	x	(x) ²⁾
Registration of concomitant treatment other than FIX replacement therapy	x	x	x	x		x	x	(x) ²⁾
Blood pressure, pulse, body temperature	x	x	x	x		x	x	(x) ²⁾
Physical examination	x	x	x	x		x	x	(x) ²⁾
Height	x							
Body weight	x	x					x	(x) ²⁾
Blood and urine sampling (see Table 5-2)	x	x	x	x	x	x	x	(x) ²⁾
Adverse events	x	x	x	x		x	x	(x) ²⁾
CCI	x						x	

Footnotes are given on next page.

Clinical Trial Protocol

Trial ID: CT-AMT-060-01

uniQure

Footnotes to [Table 5-1](#):

- 1) Time of procedures in relation to IMP administration is detailed in [Table 5-3](#).
- 2) An additional visit can be performed at any time for the purpose of conducting one or more procedures listed in the column “Additional Visits” according to the choice of the Investigator. Hence, “(x)” refers to a procedure that can be performed, if judged relevant by the Investigator.
- 3) An additional visit can be performed at any time in advance of the screening visit (i.e. Visit 1), after obtaining written informed consent, for the purpose of pre-determination of subject eligibility. For this purpose a selection of the procedures listed in the column “Additional Visits” (i.e. neutralizing antibodies to AAV5, HIV, viral load, CD4⁺, HBsAg, HBeAg, HBV DNA, HCV RNA) can be performed.
- 4) Each visit is scheduled in relation to date of IMP administration, not in relation to the date of its previous visit.
- 5) Tapering of prophylactic FIX replacement therapy may be started prior to 6 weeks after IMP administration as detailed in [Section 11.4](#).
- 6) Including available information on FIX gene mutation. If FIX gene mutation information is not available and if separate informed consent for FIX gene sequencing analysis is given by the subject, a blood sample for the purpose of FIX gene sequencing analysis should be drawn (see [Table 5-2](#)).

Clinical Trial Protocol

Trial ID: CT-AMT-060-01

Table 5-2, Flow Chart for Laboratory Parameters, Visits 1 – 21

Visit Number	1 Screening	2 Day 1	2 Day 1	2 Day 2	3 to 14 (every week)	3 ^b to 14 ^b (every week)	15 to 20 (every 2 nd week)	21	Additional visits ¹⁾
Weeks ³⁾	-6	0 Pre IMP	0 3h post IMP	0 24h post IMP	1, 2, 3, 4, 5, 6, 7, 8, 9, 10, 11, 12	1, 2, 3, 4, 5, 6, 7, 8, 9, 10, 11, 12	14, 16, 18, 20, 22, 24	26	
Visit window ³⁾			±15 minutes	±60 minutes	±2 days	1-4 days after main weekly visit	±5 days	±5 days	
Local Laboratory									
FIX: one-stage aPTT or chromogenic/amidolytic assay for FIX activity for local monitoring ⁴⁾	x	x			x	x	x	x	(x) ¹⁾
FIX inhibitors (Bethesda assay or Nijmegen modified Bethesda assay) for local monitoring and eligibility check ⁴⁾	x	x			x: Visit 14			x	(x) ¹⁾
Liver enzymes (AST/ALT)	x	x		x	x	x	x	x	(x) ¹⁾
Central Laboratory									
FIX: one-stage aPTT and chromogenic/amidolytic assay for FIX activity, and FIX protein concentration	x	x			x		x	x	(x) ¹⁾
Anti-FIX antibodies		x						x	
FIX inhibitors (Nijmegen modified Bethesda assay)	x	x			x: Visit 14			x	(x) ¹⁾
FIX recovery ⁵⁾		x							(x) ¹⁾
Total (IgM and IgG) antibodies to AAV5	x	x			x: Visits 3, 4, 5, 6			x	
Neutralizing antibodies to AAV5	x	x			x: Visits 3, 4, 5, 6			x	(x) ^{1,2)}
AAV5 capsid-specific T cells		x			x		x	x	
Sampling for vector genome detection: - Blood, urine, saliva, nasal secretions ⁶⁾ - Faeces, semen ⁶⁾		x		x	x		x	x	
Inflammatory markers IL-1 β , IL-2, IL-6, INF γ , MCP-1		x			x		x: Visits 15, 16, 17		
Haematology parameters ⁷⁾	x	x			x: Visits 6, 10, 14		x: Visits 16, 18, 20	x	(x) ¹⁾
Coagulation parameters ⁸⁾	x	x			x: Visits 6, 10, 14		x: Visits 16, 18, 20	x	(x) ¹⁾

Clinical Trial Protocol

Trial ID: CT-AMT-060-01

Visit Number	1 Screening	2 Day 1	2 Day 1	2 Day 2	3 to 14 (every week)	3 ^b to 14 ^b (every week)	15 to 20 (every 2 nd week)	21	Additional visits ¹⁾
Weeks ³⁾	-6	0 Pre IMP	0 3h post IMP	0 24h post IMP	1, 2, 3, 4, 5, 6, 7, 8, 9, 10, 11, 12	1, 2, 3, 4, 5, 6, 7, 8, 9, 10, 11, 12	14, 16, 18, 20, 22, 24	26	
Visit window ³⁾			±15 minutes	±60 minutes	±2 days	1-4 days after main weekly visit	±5 days	±5 days	
Serum chemistry parameters ⁹⁾	x	x	x ¹⁰⁾	x ¹⁰⁾	x		x: Visits 16, 18, 20	x	(x) ¹⁾
Urine parameters ¹¹⁾	x	x			x: Visits 6, 10, 14		x: Visits 16, 18, 20	x	(x) ¹⁾
HIV, viral load, CD4 ⁺	x								(x) ^{1,2)}
HBsAg, HBeAg, HBV DNA and HCV RNA	x								(x) ^{1,2)}
FIX gene sequencing ¹²⁾	x								
Blood sample for future research ¹³⁾	x	x			x: Visits 7, 12			x	

- 1) An additional visit can be performed at any time for the purpose of conducting one or more procedures listed in the column “Additional Visits” according to the choice of the Investigator. Hence, “(x)” refers to a procedure that can be performed, if judged relevant by the Investigator.
- 2) An additional visit can be performed at any time in advance of the screening visit (i.e. Visit 1), after obtaining written informed consent, for the purpose of pre-determination of subject eligibility. For this purpose a selection of the procedures listed in the column “Additional Visits” (i.e. neutralizing antibodies to AAV5, HIV, viral load, CD4⁺, HBsAg, HBeAg, HBV DNA, HCV RNA) can be performed.
- 3) Each visit and time point is scheduled in relation to date of IMP administration, not in relation to the date of its previous visit or time point.
- 4) Preferably, the same type of assay is used consistently for the individual subject throughout the entire trial period.
- 5) At Visit 2 and additionally at suspicion of FIX inhibitor or at increase in bleeding frequency, as judged by the Investigator. At each occasion a FIX challenge dose of 40 U/kg should be administered. A blood sample should be drawn just prior FIX dosing and at 30 minutes after FIX dosing.
- 6) Sampling applicable for the individual subject and for a specific matrix, only until 3 consecutive negative samples have been detected for the subject for that particular type of matrix. Based on the wish of the subject, faeces and semen samples can be collected at home prior to attending the visit (at the visit day or at the day before the visit day).
- 7) Haemoglobin, haematocrit, platelet count, red blood cells, white blood cells with differential count (all expressed in % as well as in absolute numbers).
- 8) aPTT and PT (INR). In addition, lupus anticoagulant and antithrombin will be measured at Visit 1.
- 9) Serum electrolytes (sodium, potassium), creatinine, gamma-glutamyltransferase (γGT), aspartate aminotransferase (AST), alanine aminotransaminase (ALT), alkaline phosphatase (ALP), C-reactive protein (CRP), albumin, total bilirubin, glucose (non-fasting).
- 10) Blood sample only for CRP.
- 11) pH, protein, blood, leucocyte esterase, glucose.
- 12) Only if FIX gene mutation information is not available and if separate informed consent for FIX gene sequencing analysis is given by the subject. Preferably at Visit 1, but otherwise at a later time point during the subject’s trial participation.
- 13) Only if separate informed consent is given by the subject, see also [Section 12.3.11](#).

Clinical Trial Protocol

Trial ID: CT-AMT-060-01

Table 5-3, Flow Chart for Visit 2 (Dosing Visit)

Visit	2 Day 1										2 Day 2
	Pre IMP	0	0.5	1	2	3	4	6	8	12	24
Hours after IMP infusion completed											
Inclusion/exclusion criteria	x										
Admission for overnight stay	x										
IMP infusion ¹⁾		x									
Subject e-diary instruction	x										
Subject e-diary interview (including re-instruction, if needed)	x										x
Review of e-diary data (bleeding episodes, FIX replacement therapy)	x										x
Registration of severity of bleeding episode(s)	x										x
Registration of concomitant treatment other than FIX replacement therapy	x										x
Blood pressure, pulse, body temperature	x		x	x	x	x	x	x	x	x	x
Body Weight	x										
Physical examination	x										x
Blood and urine sampling	x					x ²⁾					x ²⁾
Sampling for vector genome detection:											
- Blood, urine, saliva, nasal secretions	x										x
- Faeces, semen ³⁾	x										
Adverse events	x										x
Completion of 24 hour stay											x

1) Start time and stop time of infusion will be recorded.

2) Blood sample only for CRP.

3) Based on the wish of the subject, the pre-dose faeces and semen samples can be collected at home prior to attending the visit (at the visit day or at the day before the visit day).

Table 5-4, Flow Chart for Safety and Efficacy Evaluation, Visits 22 – 35

Visit Number	22	23	24, 25, 26	27	28, 29, 30	31	32	33	34	Additional visits ¹⁾	35 End of Trial ²⁾
Weeks ³⁾	39	52 (1 year)	65, 78, 91	104 (2 years)	117, 130, 143	156 (3 years)	182	208 (4 years)	234		260 (5 years)
Visit window ³⁾	±2 weeks	±2 weeks	±2 weeks	±2 weeks	±2 weeks	±2 weeks	±4 weeks	±4 weeks	±4 weeks		±4 weeks
Joint status		x		x		x		x		(x) ¹⁾	x
Subject e-diary interview (including re-instruction, if needed)	x	x	x	x	x	x	x	x	x	(x) ¹⁾	x
Review of e-diary data ⁴⁾ (bleeding episodes, FIX replacement therapy)	x	x	x	x	x	x	x	x	x	(x) ¹⁾	x
Registration of severity of bleeding episode(s)	x	x	x	x	x	x	x	x	x	(x) ¹⁾	x
Registration of concomitant treatment other than FIX replacement therapy	x	x	x	x	x	x	x	x	x	(x) ¹⁾	x
Blood pressure, pulse, body temperature	x	x	x	x	x	x	x	x	x	(x) ¹⁾	x
Physical examination	x	x	x	x	x	x	x	x	x	(x) ¹⁾	x
Body Weight	x	x	x	x	x	x	x	x	x	(x) ¹⁾	x
Blood and urine sampling (see Table 5-5)	x	x	x	x	x	x	x	x	x	(x) ¹⁾	x
Adverse events ⁴⁾	x	x	x	x	x	x	x	x	x	(x) ¹⁾	x
CCI		x		x		x		x			x

- 1) An additional visit can be performed at any time for the purpose of conducting one or more procedures listed in the column “Additional Visits” according to the choice of the Investigator. Hence, “(x)” refers to a procedure that can be performed, if judged relevant by the Investigator.
- 2) Since this is a gene therapy trial in which the IMP is administered to human subjects for the first time, the Investigator should make all reasonable attempts to maintain the subjects in the trial to allow long-term follow-up on safety. However, should a subject wish to withdraw from the trial, the Investigator should call the subject for the End of Trial Visit (Visit 35) to have all Visit 35 procedures conducted (unless the subject has withdrawn consent to perform any further visits).
- 3) Each visit is scheduled in relation to date of IMP administration, not in relation to the date of its previous visit.
- 4) After Visit 21 and until Visit 31 the visit frequency is every 13 weeks, and after Visit 31 and until Visit 35 (End of Trial Visit) the visit frequency is every 26 weeks. In these periods, AEs and e-diary data review will be performed at least monthly, i.e. in addition to the review at each visit. Subjects who are on continuous routine FIX prophylaxis during the long-term follow-up phase of the trial are required to contact the site staff immediately in case of a bleed and/or FIX use different from their routine FIX prophylaxis, in addition to completing the questions/information requested on the e-diaries to capture all information.

Clinical Trial Protocol
 Trial ID: CT-AMT-060-01

Table 5-5, Flow Chart for Laboratory Parameters, Visits 22 – 35

Visit Number	22	23	24, 25, 26	27	28, 29, 30	31	32	33	34	Additional visits ¹⁾	35 End of Trial
Weeks ²⁾	39	52 (1 year)	65, 78, 91	104 (2 years)	117, 130, 143	156 (3 years)	182	208 (4 years)	234		260 (5 years)
Visit window ²⁾	±2 weeks	±2 weeks	±2 weeks	±2 weeks	±2 weeks	±2 weeks	±4 weeks	±4 weeks	±4 weeks		±4 weeks
Local Laboratory											
FIX: one-stage aPTT or chromogenic/amidolytic assay for FIX activity for local monitoring ⁵⁾	x	x	x	x	x	x	x	x	x	(x) ¹⁾	x
FIX inhibitors (Bethesda assay or Nijmegen modified Bethesda assay) for local monitoring and eligibility check ³⁾		x		x		x		x		(x) ¹⁾	x
Liver enzymes (AST/ALT)										(x) ¹⁾	
Central Laboratory											
FIX: one-stage aPTT and chromogenic/amidolytic assay for FIX activity, and FIX protein concentration	x	x	x	x	x	x	x	x	x	(x) ¹⁾	x
Anti-FIX antibodies		x		x		x		x			x
FIX inhibitors (Nijmegen modified Bethesda assay)		x		x		x		x		(x) ¹⁾	x
FIX recovery ⁴⁾										(x) ¹⁾	
Total (IgM and IgG) antibodies to AAV5		x		x		x		x			x
Neutralizing antibodies to AAV5		x		x		x		x			x
Sampling for vector genome detection: Blood, urine, saliva, nasal secretions ⁵⁾	x	x	x	x	x	x	x	x	x		x
Faeces, semen ⁵⁾	x	x	x	x	x	x	x	x	x		x
Haematology parameters ⁶⁾	x	x	x	x	x	x	x	x	x	(x) ¹⁾	x
Coagulation parameters ⁷⁾	x	x	x	x	x	x	x	x	x	(x) ¹⁾	x
Serum chemistry parameters ⁸⁾	x	x	x	x	x	x	x	x	x	(x) ¹⁾	x
Urine parameters ⁹⁾	x	x	x	x	x	x	x	x	x	(x) ¹⁾	x
Blood sample for future research ¹⁰⁾		x									

Footnotes are given on next page.

Clinical Trial Protocol

Trial ID: CT-AMT-060-01

Footnotes to [Table 5-5](#):

- 1) An additional visit can be performed at any time for the purpose of conducting one or more procedures listed in the column "Additional Visits" according to the choice of the Investigator. Hence, "(x)" refers to a procedure that can be performed, if judged relevant by the Investigator.
- 2) Each visit and time point is scheduled in relation to date of IMP administration, not in relation to the date of its previous visit or time point.
- 3) Preferably, the same type of assay is used consistently for the individual subject throughout the entire trial period.
- 4) At suspicion of FIX inhibitor or at increase in bleeding frequency, as judged by the Investigator. At each occasion a FIX challenge dose of 40 U/kg should be administered. A blood sample should be drawn just prior FIX dosing and at 30 minutes after FIX dosing.
- 5) Sampling applicable for the individual subject and for a specific matrix, only until 3 consecutive negative samples have been detected for the subject in that particular type of matrix. Based on the wish of the subject, faeces and semen samples can be collected at home prior to attending the visit (at the visit day or at the day before the visit day).
- 6) Haemoglobin, haematocrit, platelet count, red blood cells, white blood cells with differential count (all expressed in % as well as in absolute numbers).
- 7) aPTT and PT (INR).
- 8) Serum electrolytes (sodium, potassium), creatinine, gamma-glutamyltransferase (γ GT), aspartate aminotransferase (AST), alanine aminotransaminase (ALT), alkaline phosphatase (ALP), CRP, albumin, total bilirubin, glucose (non-fasting).
- 9) pH, protein, blood, leucocyte esterase, glucose.
- 10) Only if separate informed consent is given by the subject, see also [Section 12.3.11](#).

6. Introduction and Rationale

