8.2.2 Secondary Endpoints

Secondary endpoints will be addressing efficacy and safety:

Confirmatory Secondary Efficacy Endpoint

- FIX-replacement-therapy-free FIX activity^{1, 2}

Supportive Efficacy Endpoints

- Bleeding rate
- Total consumption of FIX replacement therapy
- CCI scores

¹ Definition of FIX-replacement-therapy-free FIX activity: FIX activity measured any time from 72 hours after latest FIX replacement therapy administration and until next administration of FIX replacement therapy, if any

² FIX activity will be measured with both the one-stage aPTT assay and the amidolytic/chromogenic assay.

Clinical Trial Protocol

Trial ID: CT-AMT-060-01

uniQure

Safety Endpoints

- Vector DNA in semen, blood, saliva, nasal secretions, urine and faeces
- Neutralizing antibodies to AAV5
- Total (IgM and IgG) antibodies to AAV5
- AAV5 capsid-specific T cells
- Antibodies to FIX
- FIX inhibitors
- Inflammatory markers: IL-1 β , IL-2, IL-6, INF γ , MCP-1

Clinical Trial Protocol

Trial ID: CT-AMT-060-01

uniQure

9. Trial Population

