12.1 Efficacy Assessments

12.1.1 FIX Activity for Efficacy Evaluation

Blood samples for FIX activity will be collected at all visits, including at the additional visits as required during or after the tapering of prophylactic FIX replacement therapy as described in [Section 11.4](#). At Visit 2, blood sampling will take place prior to IMP administration.

Throughout the entire trial period (from Visit 1 and onwards) where a subject is on prophylactic FIX replacement therapy, it will be the aim to draw blood samples at time points where FIX activity is expected to be at the lowest levels. To the extent visit windows allow, the Investigator and/or study nurse will collaborate with the subject to schedule visits to take place on days where prophylactic FIX replacement therapy is planned to be administered. At these visits, blood sampling will then take place just prior to administration of prophylactic FIX replacement therapy, which will then be administered at the clinic instead of at home.

The following FIX activity assays will be applied at a central laboratory:

- one-stage activated Partial Thromboplastin Time (aPTT) assay
- chromogenic/amidolytic assay

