The distance between a FIX activity measurement and the latest FIX replacement therapy administration preceding the FIX activity measurement in question (c.f. section 4.4.2.1) is calculated as follows:

- date(FIX activity measurement) - date(preceding FIX replacement therapy administration) + 1

The date and time of the FIX activity measurement in question and the FIX replacement therapy administrations respectively are used to find the latest FIX replacement therapy administration preceding

Larix A/S - Strictly Confidential F501-0-1–5 SAP Template Page 13 of 34

•
ariv

CT-AMT-060-01 EudraCT No.: 2013-005579-42 Statistical Analysis Plan

Final no. 05 Page 14 of 34

the FIX activity measurement in question. In case the dates of the FIX activity measurement in question and a FIX replacement therapy administration are the same and no time is indicated, it is assumed that the FIX replacement therapy administration precedes the FIX activity measurement in question, and the above defined distance therefore becomes equal to 1 (see also section 4.4.2.1).

Duration of an AE in days is calculated (when possible) as date(Resolution) - date(Onset) + 1.

Date: 27MAY2021

No formal statistical hypothesis will be tested. Two-sided 95% confidence intervals may be calculated but these intervals represent exploratory analyses and will not be related to formal statistical hypothesis tests. No correction for multiplicity will be applied.

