## 4.4.2 Secondary Efficacy Analyses

#### 4.4.2.1 FIX Levels in Plasma

Blood samples for FIX activity will be collected at all visits. At Visit 2, blood sampling will take place prior to IMP administration.

Throughout the entire trial period (from Visit 1 and onwards) where a patient is on prophylactic FIX replacement therapy, it will be the aim to draw blood samples at time points where FIX activity is expected to be at the lowest levels. To the extent the visit windows allow, the investigator and/or study nurse will collaborate with the patient to schedule visits to take place on days where prophylactic FIX replacement therapy is planned to be administered. At these visits, blood sampling will then take place just prior to administration of prophylactic FIX replacement therapy.

The following FIX activity assays will be applied at the central laboratory:

- one-stage aPTT assay
- chromogenic/amidolytic assay

The data will be presented separately for each activity assay.

Absolute values will be listed and for each measurement the number of days since last FIX replacement therapy administration will be displayed.

The data will also be analysed descriptively by visit and cohort. These summaries will be generated both for a) all FIX measurements data b) FIX-replacement therapy free FIX measurements i.e. only measurement taken more than 10 days after the preceding FIX replacement therapy administration are included.

The procedure for calculating the above distance and defining latest FIX replacement therapy administration preceding the FIX activity measurement in question has been described in section 4.1. It is noted that if the date for a FIX replacement therapy administration is identical to the date of a FIX activity measurement and no time is indicated, then the FIX activity measurement in question is conservatively assumed to be contaminated i.e. as not FIX-replacement therapy free (the distance between the two time points will be calculated to 1 day).

For the one-stage aPTT assay data the patient individual profiles of FIX replacement free measurements in the period from last prophylactic dose (after tapering) until cut-off will also be presented. Regression lines will be presented and 95% confidence intervals will be displayed as part of legend for each patient.

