# 6 Deviations from Protocol Analysis

The protocol (section 8.2.2 defines FIX replacement therapy free FIX activity as FIX activity measured more than 72 hours after latest FIX replacement therapy. In section 4.4.2.1 the interval of 72 hours has been extended to 10 days.

Larix A/S - Strictly Confidential F501-0-1–5 SAP Template Page 29 of 34

Date: 27MAY2021

CT-AMT-060-01 EudraCT No.: 2013-005579-42

Statistical Analysis Plan

Final no. 05 Page 30 of 34

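### At Visits 22–35 no instruction times the central FIX activity draw around on-demand FIX, although the SAP excludes values within 10 days of a dose from the FIX-replacement-therapy-free summary

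*Protocol*

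**What the plan says.** **Endpoint.** Protocol 8.2.2 names FIX-replacement-therapy-free FIX activity as the confirmatory secondary efficacy endpoint and defines it as "FIX activity measured any time from 72 hours after latest FIX replacement therapy administration". SAP Section 6 records that "the interval of 72 hours has been extended to 10 days", and SAP 4.4.2.1 applies this: "only measurement taken more than 10 days after the preceding FIX replacement therapy administration are included". SAP 4.1 counts the distance as "date(FIX activity measurement) - date(preceding FIX replacement therapy administration) + 1".

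**Schedule.** After week 26, central FIX activity is drawn every 13 weeks to week 156 and every 26 weeks to week 260, which makes 14 visits (22–35). Footnote 2 to Table 5-5 reads "Each visit and time point is scheduled in relation to date of IMP administration, not in relation to the date of its previous visit". The windows are ±2 weeks at the ten visits 22–31 and ±4 weeks at the four visits 32–35.

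**Sampling and FIX dosing.** Protocol 12.1.1 states that, for a subject on prophylaxis, "it will be the aim to draw blood samples at time points where FIX activity is expected to be at the lowest levels". As far as windows allow, sites are to "schedule visits to take place on days where prophylactic FIX replacement therapy is planned to be administered". There is no counterpart for a subject off prophylaxis, although Section 11.4 expects bleeds to be treated with on-demand FIX.

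**Repeat samples.** Footnote 1 to Table 5-5 says "An additional visit can be performed at any time for the purpose of conducting one or more procedures", at the Investigator's choice, and central FIX activity is marked as optional in that column. Section 10.2.4 lists FIX activity sampling among its examples. Section 12.4 calls for a re-draw only when a result is erroneous.

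**The concern.** The SAP lengthened the washout from 72 hours to more than 10 days, but the sampling instructions did not follow. If a subject off prophylaxis treats a bleed shortly before a scheduled visit, the value drawn there does not enter the FIX-free summary. Unless the Investigator chooses to arrange an additional visit, the next draw is 13 or 26 weeks away. The window would usually have allowed a usable sample.

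The exclusion depends on outcome. Subjects who bleed more contribute fewer FIX-free values, and they are plausibly the subjects with lower expression. With about five subjects per cohort, one absent subject matters. If the mean of five is m and the absent subject's value is x, the mean of the other four is (5m − x)/4 = m + (m − x)/4. A low value that drops out therefore raises the mean by a quarter of its distance below m. The individual FIX-free regression lines in SAP 4.4.2.1 also have fewest points in these subjects.

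**Working it through.** The plan states no loss rate, so there is no figure to reproduce.

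**Inputs**
- *Excluded days (SAP 4.1).* With calendar difference d, a value is kept if d + 1 > 10. Differences of 0 to 9 are excluded, which is 10 days. Infusions on k successive days make it W = 10 + (k − 1) days.
- *Visits and windows (Table 5-5).* 10 visits at ±14 days and 4 at ±28 days.
- *Treated bleeds per year, r (assumption).* The documents give no post-treatment rate. The only anchor is the entry criterion for on-demand subjects, 4 or more bleeds in 12 months. The range shown is 1 to 12.
- *Infusion days per bleed, k (assumption).* 1 to 3.

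**Loss if the draw is on the nominal date.** With Poisson treated bleeds, P = 1 − exp(−r × W/365.25). For r = 4 and W = 10: 4 × 10/365.25 = 0.1095, and 1 − exp(−0.1095) = 10.4%. The expected number of values lost over Visits 22–35 is 14 × P.

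| r | 72-hour rule (W = 3) | k = 1 (W = 10) | k = 2 (W = 11) | Lost of 14, k = 1 | Lost of 14, k = 2 |
|---|---|---|---|---|---|
| 1 | 0.8% | 2.7% | 3.0% | 0.4 | 0.4 |
| 2 | 1.6% | 5.3% | 5.8% | 0.7 | 0.8 |
| 4 | 3.2% | 10.4% | 11.3% | 1.5 | 1.6 |
| 8 | 6.4% | 19.7% | 21.4% | 2.8 | 3.0 |
| 12 | 9.4% | 28.0% | 30.3% | 3.9 | 4.2 |

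Under the protocol's 72 hours the loss would be about a third as large.

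**Loss if the draw is postponed within the window.** A day-level simulation (100,000 runs per case) moved the draw from the nominal date to the first day that passes the SAP 4.1 count, no later than the end of the window.

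| r | ±2-week visit, k = 1 | ±2-week visit, k = 3 | Lost of 14, k = 1 | Lost of 14, k = 3 |
|---|---|---|---|---|
| 1 | 0.02% | 0.04% | 0.002 | 0.004 |
| 2 | 0.05% | 0.13% | 0.005 | 0.013 |
| 4 | 0.26% | 0.63% | 0.026 | 0.063 |
| 8 | 1.03% | 2.42% | 0.105 | 0.248 |
| 12 | 2.39% | 5.05% | 0.244 | 0.529 |

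At a ±4-week visit the remaining loss at 12 per year is 0.12% (k = 1) or 0.60% (k = 3).

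**Earlier visits.** The windows of Tables 5-1 and 5-2 are too narrow. At r = 4 and k = 1, postponement cuts a loss of 10.5% (simulated) only to 8.5% with ±2 days (Visits 3–14) and to 5.6% with ±5 days (Visits 15–21).

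**A cohort visit.** If all five subjects in a cohort were off prophylaxis and bled independently at the same rate, the chance that at least one value is missing from a visit summary (k = 1) is 1 − 0.947⁵ = 24% at r = 2 and 1 − 0.896⁵ = 42% at r = 4.

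**The case against.** The case on the other side has several parts, and most of them narrow the point.

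- *Footnote 2 read as tying visits to the dosing date alone.* A reader might infer this, but the footnote only rules out timing from the previous visit. The windows give latitude, and 12.1.1 already uses them for prophylaxis. The defect is the missing instruction for on-demand doses.
- *No way to recover the value.* Section 12.4 might suggest this, but an additional visit with a FIX activity draw is permitted at any time. What is missing is a prompt to use it.
- *Values lost outright.* They are not. Every value is listed with the days since the last FIX dose and enters the all-measurements summary. That is only a partial substitute, because the shells for that summary warn of contamination with exogenous FIX.
- *Windows wide enough throughout.* This is true only for Visits 22–35.
- *The high rates.* Section 11.4 restarts prophylaxis when FIX activity is below 2.0% and lets the Investigator restart it for medical reasons. Frequent bleeders with low expression may leave the group concerned. Section 6.2 describes prophylaxis as given 2–3 times a week, so no window helps them. This weakens the 20–30% figures and part of the bias argument.
- *No test depends on it.* Despite the confirmatory label, protocol 14.2 and SAP 4.1 plan no formal hypothesis test. The effect is on description.
- *Timing.* The first interim cut-off, set for when all subjects had 12 weeks of follow-up, was 5 August 2016. Twelve weeks earlier is 13 May 2016, and 260 weeks after that is 7 May 2021. SAP version 5 is dated 27 May 2021. By inference, nearly all of Visits 22–35 were then past, so a schedule change at that stage would recover little. The reporting change is unaffected.
- *Visit assignment.* SAP 4.7, on assessments off the exact visit date, was not in the copy reviewed. Whether an additional-visit sample would enter the by-visit table could not be checked.

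**Conclusion.** The point stands for subjects off prophylaxis at Visits 22–35. Followed as written, the plan excludes some values of its confirmatory efficacy endpoint in a way that depends on bleeding, although the existing windows could prevent nearly all of this. On nominal-date draws the loss is about 3%, 5–6% and 10–11% at 1, 2 and 4 treated bleeds per year. It reaches 20–30% at 8–12, but only if such subjects stay off prophylaxis. At up to 4 per year, postponement leaves under 1% per visit.

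These sizes rest on Poisson bleeding, assumed rates, one to three infusion days per bleed, and a baseline in which every draw falls on its nominal date.

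A reader might go further and conclude that the cohort means are biased upward. The documents do not support that as a finding. The direction is plausible, but the size is not quantified, and a return to prophylaxis may remove some poor expressers from the affected group.

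**What to change.** **Protocol 12.1.1 and a footnote to Table 5-5** (not Table 5-2): for a subject off prophylaxis who received FIX within 10 days before a planned Visit 22–35, schedule the central FIX activity draw later in the visit window, to the extent the window allows, more than 10 days after the last infusion as counted in SAP 4.1. If this is not possible, take the scheduled sample and consider the additional visit that is already permitted. FIX treatment is not to be changed for this purpose.

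**SAP 4.4.2.1:** report the number of samples excluded from the FIX-free summary per subject and visit. A lower n can then be traced to recent FIX use.

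**Cost.** Some visits move later by up to about 11 days within the existing window, with an occasional optional additional visit. Sites already review e-diary FIX use at each visit and at least monthly after Visit 21, so the information needed is at hand. It helps most if checked before the visit date is confirmed. The SAP count needs no new data.
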